6.3 Medical history

Any condition entered on the relevant medical history / current medical conditions CRF will be coded using the most updated version of MedDRA dictionary. Medical history includes heart failure history and cardiovascular disease history, and other medical history in this study, which are collected at Visit 1 (Screening visit). The number and percentage of subjects with each medical condition will be provided by treatment group and system of organ class for the ENR set and for the FAS set.

7 Study medication

7.1 Run-in phase

7.1.1 Duration of treatment exposure

The duration of the run-in study treatment exposure will be summarized (n, mean, standard deviation, minimum, Q1, median, Q3 and maximum) by treatment in a sequential manner: the valsartan run-in phase (VRS) followed by the LCZ696 run-in phase (LRS) and (frequency and

percentage of patients) by exposure duration category in each phase. The exposure duration categories are defined for each phase as:

For the valsartan run-in phase:

- 0 days
- 0 - 1 week
- 1 - 2 weeks
- >2 weeks

For the LCZ696 run-in phase:

- 0 days
- 0 - 1 week
- 1 - 2 weeks
- 2 – 4 weeks
- > 4 weeks

The valsartan run-in phase, as defined in [Section 4](#), starts at the date when the patient receives the run-in valsartan and ends at the day prior to receiving LCZ696 or when the patient discontinued, whichever comes first. The LCZ696 run-in starts at the date when the patient receives the run-in LCZ696 and ends at the day prior to randomization or when the patient discontinued, whichever comes first.

The mean duration of *each* run-in treatment phase (valsartan and LCZ696) will be computed based on each sub run-in set for overall duration and for each up-titration dose levels 1 and 2 (40 mg BID, 80 mg BID, and 80 mg matching placebo BID for valsartan; and 50 mg matching placebo BID, 100 mg matching placebo BID, and 100 mg BID LCZ696, respectively) using the following algorithm:

- Overall valsartan run-in: valsartan run-in treatment duration (days) = $\min(\text{date the patient died in run-in, date failed in valsartan run-in, date received the first run-in LCZ696 drug} - 1) - \text{date received the first run-in valsartan} + 1$;
- Overall LCZ696 run-in: LCZ696 run-in treatment duration (days) = $\min(\text{date the patient died after receiving the first run-in LCZ696, date failed in LCZ696 run-in, date randomized} - 1) - \text{date received the first run-in LCZ696} + 1$.

In each sub run-in phase:

- Run-in dose level 1 for valsartan: Run-in dose level 1 valsartan treatment duration (days) = $\min(\text{treatment start date of valsartan run-in dose level 2 medication} - 1, \text{date run-in failure date, date died}) - \text{run-in valsartan dose level 1 medication date} + 1$;
- Run-in dose level 2 for valsartan: Run-in dose level 2 valsartan treatment duration (days) = $\min(\text{treatment start date of LCZ696 run-in dose level 2 medication} - 1, \text{date run-in failure date, date died}) - \text{run-in valsartan dose level 2 medication date} + 1$;

- Run-in dose level 2 for LCZ696: Run-in dose level 2 LCZ696 treatment duration (days) = min(randomization date – 1, date failed run-in, date died) – run-in LCZ696 dose level 2 medication date + 1.

Time from the first study dose to its first top dose will also be summarized for valsartan and LCZ696, if necessary.

The above specified analysis will be repeated for the SAF to investigate the run-in drug administration profile for patients who eventually enter the double blind phase.

7.1.2 Dose level

Doses and dose levels in the run-in phase are:

Table 7-1 Study drug dispensed for the treatment run-in epoch by study visit

Study visit	Dose level	LCZ696	Valsartan
101 ^a	1	50 mg matching placebo b.i.d.	40 mg b.i.d.
102	2	100 mg matching placebo b.i.d.	80 mg b.i.d.
103	2	100 mg b.i.d.	80 mg matching placebo b.i.d.

Number and percentage of patients will be summarized by dose level (or visit) and treatment.

This analysis will be repeated for the SAF.

7.2 Double-blind phase

7.2.1 Duration of treatment exposure

The duration of the treatment exposure for a patient, regardless of temporary interruptions of usage of the study drug, is defined as

- date of last study drug intake – first study drug date (usually the randomization date) + 1.
- Duration of the treatment exposure will be summarized by treatment group descriptively (i.e. n, mean, standard deviation, min, Q1, median, Q3, max) and the number (percentage) of patients will be summarized by exposure duration category:
 - < 2 week
 - 2 to < 8 weeks
 - 8 weeks to < 4 months
 - 4 months to < 1 year
 - 1 to < 2 years
 - 2 to < 3 years
 - 3 to < 4 years
 - 4 to < 5 years
 - > 5 years.

Overall patient-years on-treatment and average patient-years on-treatment will be computed based on the duration of the treatment exposure as follow: Overall patient years

$$= \sum_{i=1}^n \text{duration of treatment exposure}_i / 365.25,$$

where n is the total number of patients in the SAF. Average patient-years on-treatment = overall patient-years on-treatment/ n . They will be summarized by treatment group.

The durations on each dose level, time from randomization to the first dose down-titration, and time from the first dose down-titration to the start of the next up-titration for patients with dose down- and up-titration will also be summarized by treatment group.

Duration of total exposure to study drug (excluding interruptions) will be computed as

- date of last study drug intake – first study drug date (usually day after randomization date) + 1 – *number of days of treatment interruption*.

The duration of total exposure to study drug will be summarized by treatment group (mean, standard deviation, median, minimum and maximum) as well as frequencies per duration category defined below.

- < 2 week
- 2 to < 8 weeks
- 8 weeks to < 4 months
- 4 months to < 1 year
- 1 to < 2 years
- 2 to < 3 years
- 3 to < 4 years
- 4 to < 5 years
- > 5 years

Percentage exposure to study drug for each patient is defined as the ratio of the total exposure to study drug divided by the treatment exposure x 100. The percentage exposure to study drug will be summarized by treatment group (mean, standard deviation, median, minimum and maximum).

The time from randomization to the permanent discontinuation of study drug, excluding treatment discontinuation caused by death, will be summarized by Kaplan-Meier curve by treatment group.

7.2.2 Dose levels

Doses and dose levels in the double blind phase are:

Table 7-2 Study drug dose levels during randomized treatment epoch

Dose level	LCZ696 Treatment Arm	Valsartan Treatment Arm
3	200 mg b.i.d.	160 mg b.i.d.
2	100 mg b.i.d.	80 mg b.i.d.
1	50 mg b.i.d.	40 mg b.i.d.

Average dose and dose level will be summarized by visit and overall study and treatment group (mean, standard deviation, median, minimum and maximum). Average dose will be calculated as, in each treatment group, at a given visit:

Sum of reported doses (including zero dose for interruption) / Total number of patients.

The formula for the average dose level is similar. The overall average (daily) dose will be calculated as:

- Daily dose for each patient = $\frac{\sum_{i=0}^3(\text{no. of days on dose level } i) \times (\text{dose level } i \times 2)}{\sum_{i=0}^3(\text{no. of days on dose level } i)}$
- Average daily dose for each patient over patients in each treatment group.

For the average overall dose level, the formula is similar, replacing “dose level $i \times 2$ ” “ by i .”

Frequency and percentage of patients at each dose level will be summarized by visit and treatment group.

The last recorded treatment on the drug administration form will be presented with the number and percentage of patients on each dose level, including off-treatment. The average dose related to the last recorded treatment will be also be summarized by treatment group, for both cases of including all patients in the SAF and excluding off-treatment patients.

7.2.3 Other exposure analyses

The number and percentage of patients with down titrations will be summarized together with the study specific reasons for down titration. This summary will be repeated for down titrations to no treatment.

The number and percentages of treatment interruption episodes and the reasons for permanent treatment discontinuation and treatment interruption episodes (any and >14 days) will be summarized by treatment group.

7.2.4 Treatment exposure in subgroups

The above treatment exposure analyses in Section 7.2.1 will be repeated for the following subgroups:

- Age group <65, ≥65 years
- Age group <75, ≥75 years
- Gender (male, female)
- Race (Caucasian, Black, Asian, Other)
- Region

- Baseline LVEF \leq , $>$ median

7.3 Study exposure

As defined before ([Section 4](#)) the double-blind study phase = the on-randomized treatment phase + the post-randomized-treatment phase. The study exposure here means the exposure for the double blind study phase. The summary of the exposure for the study phase will be computed for the FAS.

The duration of the on-treatment phase exposure (duration of study drug exposure, regardless of temporary discontinuation of study drug) will be computed for the FAS using the following formula:

- Date of last study drug intake – randomization date + 1.

The duration of the post-treatment phase will be computed for patients in the FAS who complete the last scheduled visit of the double-blind phase or have the vital status available using the following algorithm:

- Duration of the post-treatment phase (days) = date last seen (or vital status confirmed by indirect contact) - date of the visit at which the study medications was permanently stopped + 1

The overall duration of the double blind study phase will be computed for patients in the FAS.

- Duration of the double blind study phase (days) = date last seen (or vital status confirmed by indirect contact) – randomization date + 1

The durations of the on-treatment, post-treatment phase, and overall double blind study phase will be summarized by treatment group (n, mean, standard deviation, median, minimum Q1, Q3, and maximum) and the number and percentage of patients, in terms of the duration of the overall double blind study phase, will also be summarized by exposure duration category.

The study exposure duration categories are defined as

- $<$ 2 week
- 2 to $<$ 8 weeks
- 8 weeks to $<$ 4 months
- 4 months to $<$ 1 year
- 1 to $<$ 2 years
- 2 to $<$ 3 years
- 3 to $<$ 4 years
- 4 to $<$ 5 years
- $>$ 5 years

8 Concomitant medication

Medications will be identified using Novartis Drug and Therapy Dictionary, NovDTD which is a modified Novartis internal version of Q3 2004 WHO Drug Reference List (DRL) including Anatomical Therapeutic Chemical (ATC) code.

For the run-in phase, the run-in concomitant medication information will be summarized based on the ENR.

Prior and run-in concomitant medications taken at any time between the screening visit and the randomization visit will be summarized in sequential format by treatment of valsartan for the VRS and LCZ696 for the LRS based on the latest version of dictionary. Medications will be presented in alphabetical order, by ATC codes and grouped by *anatomical main group* (the 1st level of the ATC codes). Tables will show the overall number and percentage of patients receiving at least one drug of a particular ATC code and at least one drug in a particular anatomical main group.

Prior medications are defined as drugs taken prior to first dose of run-in study medication. Any medication given at least once between the day of first dose of run-in study medication and the last day prior to randomization visit will be a **run-in concomitant medication**, including those which were started pre-screening and continued into the run-in phase. Prior or run-in concomitant medication will be identified based on recorded or imputed start and end dates of taking medication. The rules for imputing incomplete (start and end) dates are described in [Section 5](#).

The concomitant medication information for the double blind phase will be summarized based on the SAF.

Concomitant medications taken at any time since the randomization visit will be summarized by treatment group based on the latest version of the dictionary. As before, medications will be presented in alphabetical order, by ATC codes and grouped by anatomical main group (the 1st level of the ATC codes). Tables will also show the overall number and percentage of subjects receiving at least one drug of a particular ATC code and at least one drug in a particular anatomical main group.

Any medication given at least once between the day of first dose of randomized study medication and the last day of study visit will be a double-blind concomitant medication, including those which were started pre-randomization visit and continued into the double blind treatment phase.

The following important classes of concomitant heart failure and CV medications administered during run-in and during double-blind phase will be summarized separately in a similar way as described above.

- ARBs
- ACE inhibitors
- Diuretics
- Beta blockers
- Aldosterone antagonists
- Cardiac glycosides (Digoxin/digitalis glycoside)

- Calcium antagonists
- Other vasodilators
- Anticoagulants
- Antiarrhythmic agents
- Aspirin
- Other antiplatelet agents
- Statins
- Nitrates
- Other lipid lowering agents

The classes of medications will be defined in a separate EXCEL sheet with ATC preferred term and WHO drug code. This EXCEL sheet will be stored in CREDI at the RAP level after the content is agreed to by the Global Program Medical Director (GPMD) and prior to CDBL

9 Efficacy evaluation

Efficacy evaluation will focus on the double blind phase and be based on the FAS. Endpoint events collected during run-in will not be utilized in the comparison of the efficacy endpoint.

The endpoint events related to the primary or secondary objectives collected during run-in will be simply summarized with adjustment for treatment exposure duration using the annualized event rates, according to the designed sequential sub-run-in periods. In case a baseline is needed for the evaluation, the run-in phase baseline will be referred to.

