3.2 Subgroup analyses

Subgroup analyses will be performed depending on the analysis purposes. Subgroups selected and types of analyses are specified in [Table 3-1](#) and will be detailed later in the sequel sections. In principle, there will be no adjustment for multiple comparisons for subgroup analyses.

4 Definitions of baseline, post baseline, analysis cut-off, and close-out

Single-blind run-in phase (Treatment run-in epoch)

The single-blind run-in phase (or run-in phase) is defined as the period between the start of the study drug (in general it should be Visit 101 or Visit 102) and the time prior to randomization (Visit 201). The run-in phase will be divided further into the valsartan run-in phase and the LCZ696 run-in phase. The start of the valsartan phase is the date the patient receives the run-in dose of valsartan. In principle, the day before a patient receives the first dose of LCZ696 (any dose level) will be the end of the valsartan run-in phase and the day the patient receives the first dose of LCZ696 will be the start day for the LCZ696 run-in phase for that patient. If the date of the start day of receiving LCZ696 is missing, then the date of Visit 103, which is the protocol specified run-in drug switching day, will be used as the start date for the LCZ696 phase. If the date of the last dose of valsartan run-in medication falls on the same day of the first dose of LCZ696 run-in medication, this day will be considered the end of the valsartan run-in phase and the following day will be considered as the start of the LCZ696 run-in phase. The LCZ696 run-in phase ends at the time when the patient receives the randomization drug. During these two run-in phases, patients will be on the run-in medications in a single blind manner.

Randomized treatment phase

The randomized treatment phase begins at the time of randomization and ends with the last study drug intake or the death of the patient, whichever comes earlier. During the randomized treatment phase, patients will return for scheduled clinic visits. For all related safety analyses randomized treatment starts with the first intake of randomized, double-blind study drug. Temporary discontinuation of the study drug will not be counted as randomized treatment phase discontinuation.

Post-randomized treatment phase

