The post-randomized treatment phase (usually after unscheduled, permanent study drug discontinuation) begins after last study drug intake + 1 day and ends on the date last seen (or vital status confirmed by indirect contact).

Double-blind (DB) phase (Randomized treatment epoch)

The double-blind phase is the combination of the randomized treatment phase and the post-randomized treatment phase.

Baseline for run-in phase

The treatment run-in baseline is defined as the last available measurement prior to or at time of Visit 101 or Visit 102, whichever is earlier. For some parameters, values may be only collected at screening (Visit 1). For them the treatment run-in baseline will be at screening.

Baseline for double blind phase

The baseline for the double blind phase is defined depending on the parameter considered. In general, the baseline for the double blind phase is defined as the last available measurement during the LCZ696 *run-in* phase and randomization (generally Visit 199 or Visit 201). For the parameters that are not designated to have measurements collected during the LCZ696 run-in or randomization, the run-in baseline may be used as the baseline for the double blind phase. The following parameters will have the double blind phase baseline at randomization visit:

NYHA class, HF signs and symptoms, vital signs, waist/hip circumference, eGFR, safety laboratory values, endpoints, 1st morning urine (sub-study patients only), lab assessments, patient global assessment (it is assumed that patients will assess their health status comparing to that at randomization), KCCQ scores and EQ-5D assessments and MMSE.

The following parameters will have their double blind phase baseline measured only at screening visit (Visit 1), i.e., prior or at Visit 101 or 102:

Height, (HF, diabetes, liver, and other) medical histories, demography, echocardiogram, and inclusion/ exclusion criteria.

NT-proBNP will be collected in all patients at Visits 1, 101/102 (whichever occurs first), 103, 199/201, 203 and 205. Additional biological markers will be collected in a subset of patients. For these biomarkers, the baseline will be defined as values at Visit 101 or 102, whichever occurs first.

Unscheduled visit

Only for the analysis of safety laboratory evaluation will unscheduled measurements be taken into account. For efficacy evaluations, measurements from unscheduled visits will generally not be used, unless specifically specified.

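### SAP 7.3 counts the post-treatment phase from the stop visit rather than the day after last intake, so a patient's two phase durations need not add up to the double-blind phase

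*SAP*

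**What the plan says.** SAP Section 4 sets the boundary between the phases at last intake. The randomized treatment phase "ends with the last study drug intake or the death of the patient, whichever comes earlier", and the post-treatment phase "begins after last study drug intake + 1 day and ends on the date last seen" or on the date vital status is confirmed indirectly. It adds: "The double-blind phase is the combination of the randomized treatment phase and the post-randomized treatment phase".

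SAP Section 7.3 refers back to Section 4 and repeats the identity: "the double-blind study phase = the on-randomized treatment phase + the post-randomized-treatment phase". It then gives three formulas:

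- On-treatment duration: "Date of last study drug intake – randomization date + 1".
- Post-treatment duration: date last seen (or vital status confirmed) minus "date of the visit at which the study medications was permanently stopped + 1".
- Overall: "Duration of the double blind study phase (days) = date last seen (or vital status confirmed by indirect contact) – randomization date + 1".

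The first and third are for the FAS. The second is "computed for patients in the FAS who complete the last scheduled visit of the double-blind phase or have the vital status available". All three are summarized by treatment group.

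**The concern.** The on-treatment formula stops at last intake and the post-treatment formula starts at a visit date. These are different dates unless something ties them together, so the phases can overlap or leave a gap, although Section 7.3 says that they add up. The stop visit is also not defined for a patient who stops between visits or reports the stop by telephone, so two programmers could derive different values from the same record.

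What is at stake is the reported length of follow-up after permanent discontinuation. A reader comparing the FAS and on-treatment results may look at it, and it would not reconcile with the other two durations in the same summary.

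**Working it through.** The SAP gives no numerical result here, so there is no figure to reproduce. The test is the SAP's own additivity rule.

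**Inputs.** R = randomization date, L = last intake, V = visit at which drug was permanently stopped, S = date last seen or vital status confirmed. The formulas are those of Section 7.3, and the phase boundaries are those of Section 4. I read Section 4 as starting the post-treatment phase on day L + 1, the reading under which the two phases meet without gap or overlap.

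**Section 7.3 as written.**

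- On-treatment = L − R + 1
- Post-treatment = S − V + 1
- Overall = S − R + 1
- Sum of the two phases = (L − R + 1) + (S − V + 1) = (S − R + 1) + 1 − (V − L)

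The discrepancy is 1 − (V − L) days, which is zero only when V = L + 1.

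**Section 4 boundaries.** Post-treatment = S − (L + 1) + 1 = S − L. The sum is (L − R + 1) + (S − L) = S − R + 1, exactly the overall duration.

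**Illustration.** Take R = day 1 and S = day 1100, so that overall = 1100 days. The gaps V − L are assumptions.

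| V − L | L | V | On-treatment | Post-treatment, 7.3 | Sum | Sum − overall | Post-treatment, Section 4 (S − L) |
|---|---|---|---|---|---|---|---|
| 0 | 500 | 500 | 500 | 601 | 1101 | +1 | 600 |
| 1 | 503 | 504 | 503 | 597 | 1100 | 0 | 597 |
| 14 | 490 | 504 | 490 | 597 | 1087 | −13 | 610 |
| 28 | 476 | 504 | 476 | 597 | 1073 | −27 | 624 |
| 84 | 420 | 504 | 420 | 597 | 1017 | −83 | 680 |
| 168 | 336 | 504 | 336 | 597 | 933 | −167 | 764 |

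For a patient whose last dose, stop visit and last contact all fall on day 1100, Section 7.3 gives 1100 − 1100 + 1 = 1 post-treatment day. Section 4 gives 0.

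**How large V − L could be.** Protocol Section 6 and Table 6-1 put contacts 12 weeks apart after Week 48, alternating telephone and clinic, so scheduled clinic visits are 24 weeks apart outside Japan. A stop midway between visits, with V taken as the next scheduled one, gives V − L = 42 days (6 weeks, next contact) or 84 days (12 weeks, next clinic visit). The shortfalls are 42 − 1 = 41 and 84 − 1 = 83 days. In year 1 the visits are at Weeks 4, 16, 32 and 48, so the longest scheduled gap is 16 weeks.

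**Partial correction.** Replacing V by L but keeping the added day gives S − L + 1, and the sum is then one day too long for every patient.

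**The case against.** The strongest objection is that the text speaks of the visit at which drug was stopped. If the stop happens at that visit, V − L is 0 or 1 and the error is one day or none. A gap of weeks arises only if V is a later visit that documents an earlier stop, which the SAP does not say. Unscheduled visits are allowed, and sites must register discontinuations with the IRT, so V need not be the next scheduled visit. Where the stop date is wholly missing and there is no fatal AE, SAP Section 5 imputes the next scheduled visit date, which may make V = L. This stands as to size: the documents fix neither V nor how often drug is stopped between visits. It does not remove the contradiction, because protocol Section 5.5.9 lets patients stop at any time and nothing sets V to L + 1.

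A second objection is that little depends on this duration. That also stands. The on-treatment and overall durations in Section 7.3 both follow Section 4, and their difference is the Section 4 post-treatment time. Section 7.2.1 adds exposure net of interruptions and a Kaplan-Meier curve of time to permanent discontinuation.

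A reader might infer three stronger things that the documents do not support:

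- That the primary or on-treatment efficacy results are distorted. The primary analysis does not use this duration, and the on-treatment LWYY analysis truncates at last intake plus 29 days (SAP 9.3.1.2).
- That off-drug time is always understated. The error is +1 day when the last dose is on the stop-visit day.
- That the duration measures all time off drug. Under either definition, temporary interruptions count as on treatment.

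**Conclusion.** The inconsistency is real and minor. Followed as written, the Section 7.3 formula departs from the Section 4 phase it is meant to measure by 1 − (V − L) days per patient: one day too many at V = L, correct at V = L + 1, and V − L − 1 days too few beyond that. This rests only on the SAP's own definitions.

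The aggregate size cannot be stated. Gaps of 6 to 12 weeks are an illustration that assumes a mid-interval stop after Week 48 and a stop visit equal to the next scheduled contact or clinic visit. They are not an estimate of what the trial will show.

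The effect is confined to one descriptive summary. Correct dates also do not guarantee that the group summaries add up, because the post-treatment duration is restricted to patients who complete the last scheduled visit or have vital status, while the other two use the FAS.

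**What to change.** In SAP 7.3, define post-treatment duration as date last seen (or vital status confirmed) minus date of last study drug intake, with no added day. Two short additions belong with it:

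- Compute the three durations in the same patients, or add a note that group summaries need not add up because the post-treatment set is restricted.
- State a rule for FAS patients who took no randomized drug. For them L does not exist, and SAP Table 2-1 removes such patients only from the safety set unless they were mis-randomized.

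The cost is one changed formula, one or two sentences in the SAP, and one derivation program. The last-intake date is already needed for Section 7.2.1 and for the on-treatment censoring, so no new data are required.
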